## **7. Risks and management associated with Ad-TD-nsIL12 therapy**

### **7.1. Potential risks**

Ad-TD-nsIL12 can cause, or is likely to cause, the following conditions:

- Systemic viral infections, such as flu-like symptoms (chills, stiffness, myalgia, arthralgia, lymphadenopathy).
- Allergic reactions, such as itching, hives, changes in blood pressure, or respiratory infections that make it difficult to breathe.
- Brain infections.
- Hepatitis, which may present with abdominal pain, jaundice, abnormal liver function tests.

Ad-TD-nsIL12 has been carefully designed to reduce its ability to cause toxic effects, but side effects are still possible. If there are signs of neurotoxicity associated with Ad-TD-nsIL12 infection, supportive care and medical treatment will be implemented as needed. Neurotoxic effects, if they occur, may be short-term. However, permanent damage is also theoretically possible. As with any clinical trial, unforeseen risks are possible. In China, many people have been exposed to AdV before and already have antibodies. If patients treated with Ad-TD-nsIL12 have never been exposed to AdV before, they may develop antibodies during the study. Although the effects of wild-type AdV on the developing embryo or fetus are known and may cause miscarriage, fetal death, fetal infection, or developmental abnormalities, there are no data on the effects of Ad-TD-nsIL12 in utero. Ad-TD-nsIL12 may enter the fetus through the placenta. Therefore, all patients and their partners are advised to use appropriate forms of contraception during their participation in this study and for 6 months after administration of Ad-TD-nsIL12. Women suspected of pregnancy during the study and needed to be checked for pregnancy status at any time.

### **7.2. Treatment of severe AdV infection**

Confirmation of the presence of AdV infection is important for deciding on antiviral agents, ruling out other treatable infections, determining prognosis, and initiating infection control measures if appropriate. If serious AdV infection is suspected after administration of Ad-TD-nsIL12, laboratory investigations such as polymerase chain reaction (PCR) and culture, analysis of cerebrospinal fluid and serum to rule out AdV infection will be performed. Other diagnostic tests such as antigen measurement, serotyping, and serology may be indicated. Additional MRI scans and brain biopsies may also be needed to determine the presence of AdV. Ribavirin, ganciclovir, cidofovir, immunotherapy, or other antiviral therapy can be started immediately, followed by appropriate treatment of the patient.

### **7.3. Treatment-related risks**

- Biopsy  
Prior to injection of Ad-TD-nsIL12, frozen sections of the tumor will be obtained to confirm the diagnosis of DIPG. If encephalitis is suspected, stereotactic biopsy may be performed to assess the presence of Ad-TD-nsIL12 or wild-type AdV infection or, if necessary, to confirm tumor progression. Risks of brain biopsy include hemorrhage, hematoma, infection (local infection, brain abscess, meningitis), fever, pain, increased intracranial pressure, general decline in consciousness, focal neurologic deficits (e.g.,

weakness, loss of sensation, speech disturbance, aphasia, memory loss, loss of vision, diplopia, loss of cognitive function), seizures, stroke, coma, and death.

- Tumor resection
 

The risks associated with craniotomy and tumor removal are varied, including but not limited to pain, hemorrhage, hematoma, epilepsy, stroke, infection, fever, decreased level of consciousness, focal neurological deficits (eg, weakness, sensory loss, speech impairment, aphasia, memory loss, vision loss, diplopia, and any other deficit of brain function, complete or partial loss of cognitive function), coma, and death. In addition, there are non-neurologic risks that can arise from any surgery or anesthesia (including, but not limited to, respiratory failure, pneumonia, cardiac arrest, myocardial infarction, pulmonary embolism, deep vein thrombosis).
- MRI
 

Risks associated with MRI include claustrophobia and anxiety reactions. Reactions to the contrast medium gadolinium include; Nausea, headache, hot flashes, and palpitations. Allergic reactions to gadolinium include: skin rash, urticaria, dyspnea, in extreme cases, anaphylactic shock and possible death. Individuals with any contraindications to MRI (e.g., pacemakers, epicardial pacemaker lines, infusion pumps, surgical and/or aneurysm clips, shrapnel, metal prostheses, potentially magnetic implants, metal objects in the eye, etc.) will not be included. In addition, individuals with tumors that cannot be assessed by MRI will not be eligible for the study.
- Encephalitis
 

Postoperative fever is not uncommon. However, fever of  $\geq 38.9^{\circ}\text{C}$  (with or without seizures) lasting  $\geq 48$  hours, decreased neurologic status and increased areas of hemorrhagic necrosis outside the tumor boundary on MRI, may indicate viral encephalitis. When appropriate, stereotactic biopsy should be performed to determine the presence of Ad-TD-nsIL12 or AdV (wild-type). The procedure of a biopsy involves taking a sample of tumor tissue through a biopsy needle and sending it to a hospital laboratory for testing. Biopsy specimens undergo standard hematoxylin and eosin (H&E) staining, as well as immunostaining. In addition, if the specimen is sufficient, tests such as PCR and culture to detect AdV and Ad-TD-nsIL12 will be performed. The pathologist will review the processed biopsy tissue. Antiviral therapy is given as appropriate.
- Focal neurological deficits
 

Decreased neurological status (eg, decreased mental status), including focal neurologic deficits or specific neurologic deficits (paralysis, speech impairment, depending on tumor location), can be attributed to tumor progression, edema, hemorrhage, hydrocephalus, or encephalitis. CT and, if appropriate, MRI to help determine the cause of these neurological changes.
- Hemorrhage
 

PT/INR, PTT, and platelet count are measured. Small hematomas can be treated conservatively. Large haematomas or hematomas associated with progressive neurological deterioration (i.e. > grade 3) may require surgical hematoma removal and decompression. The acceptable degree of neurotoxicity secondary to hematoma is (CTC < grade 3).
- Increased intracranial pressure

Symptoms in patients with mass masses may be related to increased intracranial pressure. Symptoms may worsen, especially after an injection of Ad-TD-nsIL12. For more extreme cases, standard treatment includes dexamethasone or mannitol.

- Necrotizing meningitis  
Response to Ad-TD-nsIL12 may cause inflammation or meningeoid symptoms. Symptoms may be self-limited and controlled with steroids and/or analgesics, but in some cases may be severe enough to cause nerve damage or death. To exclude infection, it may be necessary to perform a lumbar puncture.
- Cerebral edema  
Cerebral edema usually occurs postoperatively in patients with tumors and usually requires standard measures to treat elevated intracranial pressure. Edema may be secondary to the disease process, surgical process, necrosis and inflammation, viral particles, metastatic tumor cells. Symptoms may include, but are not limited to, severe headache, confusion, lethargy, unresponsiveness, or focal neurological deficits. Participants generally take prophylactic high-dose steroids, but the dose may need to be increased. Edema that does not respond to aggressive treatment can lead to permanent nerve damage.
- Infection  
Any surgical procedure carries a risk of infection. This risk may be increased by injecting the virus.
- Other risks

## **8. Adverse event (AE)**

### **8.1. Document of adverse events**

All AEs will be recorded in a Case Report Form (CRF), either during clinical follow-up or voluntarily reported by the patient and their families, and graded according to NCI-CTCAE v5.0. If the investigator determines that a dose-related SAE (grade 3-4) has occurred, the safety committee will evaluate the AE and make changes to the admission of subsequent patients or even stop the recruitment of subsequent participants. AE is recorded until 12 weeks after viral injection as required by the protocol.

### **8.2. Time to collection of adverse events**

Collection of all AEs will begin on the day of virus injection. If investigators believe an event is relevant to this study, the event should be collected at any time after using the study product.

### **8.3. Definition of adverse events**

Refer to the occurrence or worsening of any adverse medical event (e.g., signs, symptoms, disease, syndrome, intercurrent illness, abnormal laboratory findings) relative to baseline levels following the administration of an intervention (pharmacotherapy). AE is not necessarily causally related to drug use. Therefore, AE can be any adverse and/or unexpected sign (including abnormal laboratory results), symptoms, and diseases that are not associated with drug use. Common events/symptoms during surgery (e.g., pain, headache, changes in standard blood pressure, constipation, etc.) are usually within the normal range. Long-term, latent, disease-related conditions that have not changed from baseline are not considered AEs. Exacerbations of underlying chronic conditions will be assessed for their "severity" and, if determined to be "severe," will be reported as SAE at the appropriate location on the form. SAE includes the following:

- Fatal
- Life-threatening

- Request or extend hospital stay
- Disability
- Can cause congenital anomalies/birth defects

In addition, any significant medical event can and should be reported to the sponsor as a SAE if deemed necessary by the principal investigator.

#### **8.4. Grade of adverse events and relevance of study drugs.**

- Level 1: Unrelated
- Level 2: Unlikely
- Level 3: Possible
- Level 4: Likely
- Level 5: Certain

The association between adverse events and Ad-TD-nsIL12 will be determined by the principal investigator, and any level 4 or 5 association will be considered relevant to the treatment of Ad-TD-nsIL12.

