#### **4.8. Dose escalation and determination of the maximum tolerated dose**

**(MTD).**

- The dose will start with  $3 \times 10^9$ vp. Three dose stages are planned:  $3 \times 10^9$ vp,  $1 \times 10^{10}$ vp as well  $3 \times 10^{10}$ vp.
- Each cohort will include 3 to 6 participants depending on the occurrence of AE. The criteria for dose climbing are as follows:
  - If there were no Ad-TD-nsIL12 related SAEs (NCI-CTCAE  $\geq$  grade 3) occurred within 6 days after virus injection in the previous patient in the same cohort, the latter patient continues to be included.
  - If 1 patient developed Ad-TD-nsIL12 related SAE in a cohort, 3 patients will continue to be included in this cohort to verify whether it's accidental, and if any 1 of the subsequent 3 patients developed Ad-TD-nsIL12 related SAE, it would be considered as the dose limiting toxicity (DLT), and the previous dose is taken as the maximum tolerated dose (MTD).
  - If 2 patients in the same cohort developed investigational drug-related SAE, it will be considered to be DLT, then the trial will be terminated and the dose used in previous cohort will be defined as MTD.
  - If all 3 patients in the same cohort had no drug-related SAE within 10 days after virus injection, the dose would be upgraded to the next cohort.
  - If DLT presented in the first cohort (D1), dose adjustment will be made according to what is described in protocol 4.3, and if DLT still occurs at D0, the trial terminates.
  - If DLT still does not occur at the highest dose D3, MTD is not defined and the trial terminates.
- Any clinical SAEs deemed to be likely to be associated with Ad-TD-nsIL12 will be recorded by the investigator and graded accordingly. Follow-up will continue until the SAE disappears or drops to grade 1.
- In addition, if non-neurological complications related to any surgical or anesthesia management occur (including, but not limited to, respiratory failure, pneumonia and other systemic infections, cardiac arrest, myocardial infarction, pulmonary embolism, deep vein thrombosis, tracheal and laryngeal trauma, postanesthesia lethargy, fatigue, and short-term memory loss), dose reduction may be considered after discussion with the principal investigator.

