### **10.3.Safety**

Patients who do not complete the study, for any reason, will include all available data prior to termination of the study in the safety analysis. AEs will be summarized by population and dose group, and tabulated by severity, relationship with Ad-TD-nsIL12, and causation. In addition, SAEs, AEs that may be related to Ad-TD-nsIL12, and AEs that are not related to Ad-TD-nsIL12 will be aggregated separately. Concurrent conditions will be listed and may be identified as possible confounding factors in the treatment-response relationship. Follow-up and treatment for AE will also be documented. Summary data includes univariate statistics for mean, standard error, percentage, and median. AE-related clinical laboratory results will provide descriptive statistics on selected laboratory parameters based on population, patients, study dates, and dose groups.

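### A grade 3 or higher SAE rated Possible is outside the DLT count under 8.4 and 4.8 but inside the D1 rule in 4.3, and 10.3 does not say where it belongs

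*Protocol*

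**What the plan says.** Four places in the protocol bear on this.

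- **Section 8.4** gives a five-level association scale whose middle category is "Level 3: Possible". The principal investigator assigns the level, and "any level 4 or 5 association will be considered relevant to the treatment of Ad-TD-nsIL12". Level 3 is left outside.
- **Section 4.8** introduces the event that drives the dose decisions as "Ad-TD-nsIL12 related SAEs (NCI-CTCAE", with a threshold of grade 3 or higher. After one such event, three more patients enter, and "if any 1 of the subsequent 3 patients developed Ad-TD-nsIL12 related SAE, it would be considered as the dose limiting toxicity (DLT". With two events: "If 2 patients in the same cohort developed investigational drug-related SAE, it will be considered to be DLT". Escalation requires that all three patients "had no drug-related SAE within 10 days after virus injection, the dose would be upgraded to the next cohort". The section also states: "Any clinical SAEs deemed to be likely to be associated with Ad-TD-nsIL12 will be recorded by the investigator".
- **Section 4.3** gives the rule at D1. Two or three patients with an SAE by CTCAE lead to the lower dose D0, and one leads to three more patients at D1. No relatedness condition is attached.
- **Section 10.3** describes the tables: "AEs that may be related to Ad-TD-nsIL12, and AEs that are not related to Ad-TD-nsIL12 will be aggregated separately". It also tabulates AEs by relationship to the drug.

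Section 10.1 makes the MTD the primary endpoint and derives it from DLT.

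**The concern.** The MTD rests on how many patients in a cohort of three to six have a counted event, so the attribution cut is part of the decision rule. Reclassifying one event turns 1 of 3 (expand) into 0 of 3 (escalate), or 2 of 6 (DLT) into 1 of 6 (no DLT).

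In this trial *Possible* is a plausible rating for the events that matter. Under 4.3 the virus is given immediately after stereotactic biopsy and reservoir insertion. Section 7.3 attributes neurological decline to tumor progression, edema, hemorrhage, hydrocephalus or encephalitis, calls postoperative fever not uncommon, and traces edema to disease, surgery, inflammation or viral particles. An investigator facing such an event may reasonably stop at level 3.

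Two things are then at stake. The same event at D1 is treated differently depending on which section is followed. And if some *Possible* events are truly caused by the drug, the count in 4.8 misses them and the design escalates more readily than its rule suggests.

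**Working it through.** **The plan's own figure.** Section 1.6 gives 9-18 patients. Three cohorts of three give 3 × 3 = 9, and three cohorts of six give 3 × 6 = 18. The figure reproduces and does not depend on the attribution cut.

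**Where a level 3 SAE of grade 3 or higher falls**

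| Section | Cut used | Counts? |
|---|---|---|
| 8.4 with 4.8 | levels 4-5 | no |
| 4.3, at D1 | none stated | yes, as worded |
| 10.3 | may be related / not related | not stated |

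**Effect on escalation.** Let q be the probability that a patient has a counted event. I take 4.8 to allow escalation after 0 of 3, or after 1 of 3 followed by 0 of 3. The second route is implied by the purpose of the expansion rather than spelled out.

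P(pass) = (1−q)³ + 3q(1−q)² × (1−q)³

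The protocol gives no target DLT rate and no expected share of *Possible* ratings, so both are assumed. The separate D1 wording in 4.3 and the step to D0 are not modelled.

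*Drug-caused events lost.* Let p be the true rate of drug-caused grade 3 or higher SAEs and f the share rated only *Possible*. Then q = p(1−f).

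Example, p = 1/3:
- f = 0: q = 1/3, P = 0.2963 + 0.4444 × 0.2963 = 0.428
- f = 50%: q = 1/6, P = 0.5787 + 0.3472 × 0.5787 = 0.780

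| p | f = 0 | f = 25% | f = 50% | f = 75% |
|---|---|---|---|---|
| 0.20 | 0.709 | 0.814 | 0.906 | 0.973 |
| 1/3 | 0.428 | 0.600 | 0.780 | 0.932 |
| 0.50 | 0.172 | 0.351 | 0.600 | 0.862 |

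*Across all three doses.* With assumed true rates of 0.10, 0.25 and 0.45 at D1, D2 and D3, the chance that the trial passes D3 with no MTD defined is the product of the three pass probabilities. It is 0.127 at f = 0, 0.292 at f = 25% and 0.549 at f = 50%.

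*Unrelated events gained.* Suppose instead that level 3 counts, and that independent procedure or tumor SAEs rated *Possible* occur at rate u. Then q = 1 − (1−p)(1−u). With p = 0.10:
- u = 0: q = 0.10, P = 0.729 + 0.243 × 0.729 = 0.906
- u = 10%: q = 1 − 0.9 × 0.9 = 0.19, P = 0.730
- u = 20%: q = 1 − 0.9 × 0.8 = 0.28, P = 0.536

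Either cut can therefore move the MTD, in opposite directions.

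**The case against.** The strongest reply is that a threshold at *Likely* is a stated design choice. Sections 8.4 and 4.8 agree on it, since 4.8 itself speaks of SAEs likely to be associated with the drug. This stands: the threshold is not in itself an error, and the calculation above shows that a wider cut has a real cost.

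A second reply is that 4.8 sends the reader to 4.3 only once a DLT has occurred at D1, so relatedness might be carried over. That reading is possible. But 4.3 states its own trigger, in terms of SAEs by CTCAE and without that condition, so two sites or two readers could act differently on the same event.

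Three stronger readings are tempting, and the documents do not support them.

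- *A Possible event can never affect the dose.* It can at D1 under 4.3 as worded. Section 4.8 also lets dose reduction be considered after non-neurological surgical or anesthesia complications.
- *The MTD is biased upward.* This needs some *Possible* events to be drug-caused. With f = 0 there is no shift, and the documents give no value for f.
- *Section 10.3 contradicts 8.4.* Section 10.3 is descriptive, and a reporting cut may differ from a DLT cut. It uses different words and leaves level 3 unmapped, which is an ambiguity rather than a contradiction.

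**Conclusion.** The point holds in a limited form. Followed as written, 8.4 and 4.8 leave *Possible* SAEs of grade 3 or higher out of the count that sets the primary endpoint. Section 4.3 includes them at D1, and 10.3 does not place them. These are facts of the text.

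The size is conditional. With an assumed true rate of 1/3, the chance of passing the dose rises from 0.43 to 0.60, 0.78 or 0.93 if a quarter, half or three quarters of drug-caused events are rated *Possible*. With an assumed 10% true rate, counting level 3 lowers it from 0.91 to 0.73 or 0.54 if unrelated *Possible* events occur in 10% or 20% of patients. All these rates are assumptions. They show that the MTD can depend materially on attribution, not by how much it will in this trial. A reader might infer that levels 3-5 must be the DLT cut. The documents do not settle that, and the choice belongs to the sponsor and investigator.

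**What to change.** The sponsor and investigator should reconcile 4.3, 4.8 and 8.4 so that one explicit set of association levels counts toward DLT at every dose, including D1. Section 10.3 should say on which side level 3 falls, or show it as its own category.

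In addition, report the DLT count per cohort and the resulting MTD under both cuts, levels 4-5 and levels 3-5, as a sensitivity analysis. The data will be available, since 8.1 has all AEs recorded in the CRF. A cohort run under one cut may be incomplete under the other, for example 1 of 3 without expansion. In that case give the count and say that the MTD is not determined under that cut.

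The cost of stating the rule consistently and reporting both cuts is a small amount of extra reporting, and possibly two differing MTD readings to discuss. If the reconciliation changes which levels count, the design's escalation probabilities change as shown above, and that should be weighed before the wording is fixed.

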#### **8.5. Unexpected adverse events**

Any drug will be inconsistent with the specificity or severity of the drug described in the current investigator's manual.

#### **8.6. Report of serious adverse events**

All accidental, life-threatening or fatal incidents related to the research product must be reported in writing to the project sponsor within 24 hours of the event (the next business day). All SAEs defined in the protocol that are considered drug-related must submit a written report to the program sponsor within 5 business days of occurrence. Serious adverse effects must be followed until clinical recovery is complete, laboratory testing returns to baseline, the progression of the event has stabilized, or the event has been acceptably resolved.

### **9. Ethics**

#### **9.1. Ethical considerations**

- The protocol and all the required documents attached will be submitted to the Ethics Committee of Sanbo Brain Hospital, Capital Medical University for approval before starting the study. Any modifications to the protocol will be submitted to the ethics committee for approval.
- All patients in this study will be given a consent form describing this study and will be provided with sufficient information to allow participants to make a decision about their participation in this study. This consent will be submitted with the protocol for review and approval by the ethics committee.

#### **9.2. Information provided to patients and informed consent**

- All participants in this study will be given a consent form describing this study and provided with sufficient information to make a decision about their participation in this study. Before the patient join any study procedure, formal consent must be obtained from the patient or a legally acceptable agent using an approved consent form. The procedure will be carried out in accordance with ICH specifications. The investigator will retain the informed consent form in the investigator's file.
- Patients under the age of 12 do not have to sign an informed consent form, and they will listen to information about the treatment protocol in order to participate in decision-making and understand treatment options. The patient's parents will sign an informed consent form. Patients over the age of 12 can sign an informed consent form with parents' signature.
- Patients and parents will be informed that participation is voluntary and can

withdraw from the study at any time without any impact on future medical care.

- The informed consent form shall not modify the information content without the written approval of the ethics committee and the sponsor.
- The informed consent form includes information about the need to review medical records and informs the patient that stored laboratory samples (e.g., blood, tissue, etc.) will be used for analysis in the future, and that additional blood tests and preserved tumor tissue samples will be used for genotyping and tissue bank storage as appropriate.

